Background and Rationale: Neisseria meningitidis is a leading cause of bacterial meningitis and sepsis worldwide, capable of causing outbreaks and epidemics of invasive disease. Meningococcal disease is associated with high morbidity and mortality even among patients who receive early antibiotic treatment. Most cases of invasive disease worldwide are caused by serogroups A, B, C, W and Y. The quadrivalent meningococcal oligosaccharide diphtheria CRM-197 conjugate vaccine (MenACWY-CRM; Menveo, GSK Vaccines) is approved for active immunization of individuals from 2 months through 55 years of age in the United States, and in over 60 other countries. As of February 2015, more than 30,000 of subjects have been exposed to MenACWY-CRM vaccine in completed clinical studies and more than 24 million doses of the vaccine have been distributed globally. The US Advisory Committee on Immunization Practices (ACIP) recommends routine vaccination with a quadrivalent conjugated meningococcal vaccine for adolescents at 11-12 years of age with a booster dose administered 5 years later. While a substantial body of data exists showing a robust immune response and good antibody persistence after a single dose of MenACWY-CRM in adolescents, the response to a booster dose of MenACWY-CRM in this age group has only been evaluated in 2 clinical studies with limited number of subjects. A robust anamnestic immune response to a booster dose of Menveo vaccine administered at approximately 5 years after previous vaccination with the same vaccine or a licensed meningococcal polysaccharide vaccine (Menomune®) was demonstrated in		

Name of Sponsor:	Protocol number:	Gene 1 c name of study vaccine(s):
GlaxoSmithKline Biologics S.A	V59 77	Meningococcal (groups A, C, W, and Y) oligosaccharide diphtheria CRM-197 conjugate vaccine

the phase 2 clinical study V59P6El . High titers of bactericidal antibodies against the vaccine serogroups were achieved at 7 and 30 days after booster dose in MenACWY-primed subjects. However, the number of subjects included in this study was relatively small (N=101 , including 50 subjects who received a booster dose **after** the primary MenACWY-CRM vaccination).

In the phase 3b clinical study V59P13 E1 , a booster dose of MenACWY-CRM was given 3 years **after** primary vaccination with either MenACWY-CRM or Menactra®(a meningococcal diphtheria toxoid-conjugated MenACWY vaccine, MenACWY-D) in adolescents. A booster dose was able to substantially increase antibody titers against all 4 serogroups irrespective of the priming vaccine. Again, only a small number of subjects (N=160) received the MenACWY-CRM booster, (83 who received **primary** MenACWY-CRM and 77 who received MenACWY-D).

In the light of the current ACIP recommendation for a booster dose of MenACWY-CRM, there exists a need to evaluate the response to a MenACWY-CRM booster given at -5 years **after** primary vaccination in meningococcal vaccine primed adolescents. Generation of this data would also be of relevance in outbreak management and vaccination of travelers to endemic areas.

The purpose/aim of this study is to assess the safety and antibody response to vaccination with a booster dose of Menveo given 4-6 years **after primary** vaccination and the response to a single dose given to vaccine-naïve subjects, and to describe the immune response over time after a booster dose of Menveo, administered to subjects previously vaccinated with Menveo or Menactra, and **after** a single dose of Menveo to vaccine-naïve subjects. The inclusion of vaccine-naïve subjects in a separate study arm is to enable comparison of the rapidity and magnitude of an anamnestic response to a booster dose (in primed individuals) or the **primary** response to a **first** dose (in naïve individuals) of MenACWY-CRM.

Study Objectives:

Primary Objective(s): Immunogenicity objective:

1. To demonstrate a sufficient immune response following a booster dose of MenACWY-CRM (Menveo) vaccine, given to subjects who previously

Name of Sponsor:	Protocol number:	Generic name of study vaccine(s):
GlaxoSmithKline Biologicals S.A	V59 77	Meningococcal (groups A, C, W, and Y) oligosaccharide diphtheria CRM-197 conjugate vaccine

received Mencevo, as measured by the percentage of subjects with hSBA seroresponsel against N. meningitidis serogroups A, C, W and Y at Day 29 after vaccination
 
2. To demonstrate a sufficient immune response following a booster dose of MenACWY-CRM (Mencevo) vaccine, given to subjects who previously received Menactra, as measured by the percentage of subjects with hSBA seroresponsel against N. meningitidis serogroups A, C, W and Y at Day 29 after vaccination
 
Criteria to demonstrate immune response sufficiency The immune response sufficiency will be tested sequentially; first in the group of subjects who received primary vaccination with Mencevo and, if met, also in the group of subjects who received primary vaccination with Menactra. The immune response will be considered as sufficient if the lower limit of the one-sided 97.5% CI for percentage of subjects with hSBA seroresponse¹ against serogroups A, C, W and Y is greater than 75%. The study will be considered successful if the immune response sufficiency will be demonstrated at least in the group of subjects who received primary vaccination with Mencevo.
		

Secondary Objective(s):
 
Immunogenicity objectives:
 
1. To compare the immune responses over time following a booster dose of MenACWY-CRM vaccine, between subjects who previously received Mencevo, subjects who previously received Menactra, and subjects who previously received Mencevo or Menactra (pooled vaccine group) and following a single dose in vaccine-naive individuals, as measured by the percentages of subjects with hSBA seroresponsel hSBA titers, 1:8 and 1:16, and hSBA GMTs against N. meningitidis serogroups A, C, W and Y at Day 1, Day 4, Day 6 and Day 29
		

¹ Seroresponse is defined for this study as follows: For subjects with pre-vaccination titers <4, post-vaccination titers 2:16; for subjects with pre-vaccination titers 2:4, post-vaccination titers at least 4 times the pre-vaccination titers.

Name of Sponsor:	Protocol number:	Generic name of study vaccine(s):
GlaxoSmithKline Biologicals S.A	V59 77	Meningococcal (groups A, C, W, and Y) oligosaccharide diphtheria CRM-197 conjugate vaccine
after vaccination		
2. To assess persistence of bactericidal antibodies against serogroups A, C, W and Y at approximately 4-6 years after the primary vaccination with Menveo and after the primary vaccination with Menactra in comparison with naturally-acquired levels in vaccine-naïve individuals as measured by the percentages of subjects with hSBA titers 8 and hSBA GMTs at Day 1.		
Safety objectives:		
1. To assess reactogenicity and safety of MenACWY-CRM vaccine when administered to subjects who previously received Menveo or Menactra and vaccine-naïve individuals.		
Study Design:		
This is a phase 3b, controlled, open-label, multi-center study to evaluate safety and immunogenicity of MenACWY-CRM after a single vaccination in healthy individuals who were vaccinated with Menveo or Menactra 4 to 6 years before and in vaccine-naïve individuals.		
Study population Approximately 700 healthy subjects 15 through 55 years of age will be enrolled in the study.		
Duration of the study The duration of this study is approximately 6 months per subject.		
Written informed consent and, as applicable according to local guidelines, written assent will be obtained before conducting any study-specific procedures.		
Vaccination schedule: All subjects will receive a single dose of MenACWY-CRM at Day 1.		
Study groups:		

Group Menveo-Menveo: approximately 300 subjects, who were vaccinated with a single dose of Menveo 4 to 6 years before, will receive one dose of MenACWY-CRM.Group Menactra-Menveo: approximately 300 subjects, who were vaccinated with a		

Name of Sponsor:	Protocol number:	Generic name of study vaccine(s):
GlaxoSmithKline Biologics S.A	V59_77	Meningococcal (groups A, C, W, and Y) oligosaccharide diphtheria CRM-197 conjugate vaccine

single dose of Menactra 4 to 6 years before, will receive one dose of MenACWY-CRM.

- Group Naive: approximately 100 subjects, of similar age to subjects enrolled in other primed groups, with enrolment distributed across all clinical sites, who have not received any meningococcal vaccination, will receive one dose of MenACWY-CRM.

Randomization / Stratification:

Within each study group, subjects will be randomized into one of two different blood draw schedules according to a 1:1 ratio, described as follows:

- Subjects getting blood draws at Day 1, Day 4 and Day 29.
- Subjects getting blood draws at Day 1, Day 6 and Day 29.

For a schematic overview, see Table 1.

Table I: Schematic diagram of the V59_77 study groups

Vaccine History	Vaccination in current study	Blood draw schedule
Menveo N=300	Menveo	Blood draw Day 1, 4, 29 (N=150)
		Blood draw Day 1, 6, 29 (N=150)
Menactra N=300	Menveo	Blood draw Day 1, 4, 29 (N=150)
		Blood draw Day 1, 6, 29 (N=150)
Vaccine-Naive N=100	Menveo	Blood draw Day 1, 4, 29 (N=50)
		Blood draw Day 1, 6, 29 (N=50)

Blinding open-label study.

Blood samples: Three (3) blood samples of approximately 10 mL each will be collected according to the blood draw schedule in Table 1.

Data collection: Electronic Case Report Form (eCRF).

Study clinic visits: Three (3) clinic visits at Day 1, Day 4 or Day 6 and Day 29 are

Name of Sponsor:	Protocol number:	Generic name of study vaccine(s):
GlaxoSmithKline Biologics S.A	V59 77	Meningococcal (groups A, C, W, and Y) oligosaccharide diphtheria CRM-197 conjugate vaccine

planned for each subject.

Reminder Phone calls: Two (2) reminder phone calls will be conducted at Day 3 and Day 5 after the study vaccination to remind the subject/legal guardian to complete the diary card.

Safety phone calls: Three (3) safety phone calls (at Day 15, Day 91 and Day 181) will be conducted to collect any medically-attended AEs, AEs leading to withdrawal, SAEs, related medications and any vaccinations. In addition, all unsolicited AEs and related medications occurring after the vaccination will be collected during the safety call at Day 15. The Day 181 Safety Phone call will also serve as the termination visit.

Solicited Adverse Events (injection site pain, erythema, induration, fatigue, headache, myalgia, arthralgia, loss of appetite, nausea, chills and fever) occurring on the day of vaccination and the following six days (Day 1 through Day 7) will be recorded daily using a Diary Card for all subjects.

Unsolicited AEs occurring within 28 days after study vaccination will be collected. Qualified site staff will interview the subject by phone approximately 14 days after vaccination and in person at the study site approximately 28 days after study vaccination to assess the occurrence of any unsolicited AEs.

Medically-attended AEs, AEs leading to study withdrawal and SAEs will be collected during the entire study period. These data will be captured by interviewing the subject and/or subjects' parents / guardian (as applicable) during the site visits and phone calls and by review of available medical records. Subjects and/or parents / guardian will be encouraged to call the site in the event of any medically-attended AEs or any AEs which they perceive as being of concern during the entire study period.

Table 2: Schematic diagram of the V59_77 study design.

Day 1	Day 4	Day 6	Day 15	Day 29	Day 91	Day 181
Blood draw (all subjects) Menveo	Blood draw (50% of subjects)	Blood draw (50% of subjects)	Safety Phone call	Blood draw (all subjects)	Safety Phone call	Safety Phone call Study termination

Number of Subjects planned: Approximately 700 subjects are planned for enrolment

Name of Sponsor:	Protocol number:	Generic name of study vaccine(s):
GlaxoSmithKline Biologics S.A	V59_77	Meningococcal (groups A, C, W, and Y) oligosaccharide diphtheria CRM-197 conjugate vaccine
into this study, approximately 300 subjects who previously received Menveo (Menveo-Menveo group), 300 subjects who previously received Menactra (Menactra-Menveo group) and 100 meningococcal vaccine-naive subjects (Naive group). Assuming a 10% drop-out rate that should provide approximately 630 evaluable subjects.		
Study Population and Subject Characteristics: The list of inclusion and exclusion criteria is included in protocol section 4, Selection of Study Population .		
Study Procedures: The study includes three clinic visits, one vaccination, three blood draws, and three safety phone calls for each subject. All study procedures associated with the pre-vaccination, vaccination, post-vaccination and study termination visit are described in section 5.0 .		
Study Vaccines: GlaxoSmithKline Meningococcal MenAC\1VY- CRM191 vaccine (Menveo): Meningococcal (groups A, C, W and Y) oligosaccharide diphtheria CRM-197 conjugate vaccine is supplied as a vial that contains 10 µg of serogroup A oligosaccharides and 5 µg of serogroups C, W and Y oligosaccharides, conjugated to Corynebacterium diphtheriae CRM191 protein. Overall injection volume of 0.5 mL. The vaccine will be administered intramuscularly, preferably in the deltoid area of the non-dominant arm.		
Primary Endpoint(s): Immunogenicity Endpoints: The following measures will be summarized for Menveo-Menveo and Menactra-		

Name of Sponsor:	Protocol number:	Gene1ic name of study vaccine(s):
GlaxoSmithKline Biologics S.A	V59 77	Meningococcal (groups A, C, W, and Y) oligosaccharide diphtheria CRM-197 conjugate vaccine

Menveo groups:

1. Percentage of subjects with hSBA seroresponse¹ against *N. meningitidis* serogroups A, C, W and Y at Day 29.

Secondary Endpoints:

Immunogenicity endpoints:

The following measures will be summarized for Menveo-Menveo, Menactra-Menveo, Naive and the pooled (Menveo-Menveo and Menactra-Menveo) groups:

1. Percentage of subjects with hSBA titer 2:8 and 2:16 against *N. meningitidis* serogroups A, C, W and Y at Day 1, Day 4, Day 6 and Day 29 and between-group differences;
2. Percentages of subjects with hSBA seroresponse² against *N. meningitidis* serogroups A, C, W and Y at Day 4, Day 6 and Day 29 and between-group differences;
3. hSBA GMTs against *N. meningitidis* serogroup A, C, W and Y at Day 1, Day 4, Day 6 and Day 29;
4. Ratios of hSBA GMTs at Day 1, Day 4, Day 6 and Day 29 (between study groups).
5. hSBA Geometric Mean Ratios (G:MRs) at Day 4, Day 6, and Day 29 compared to Day 1 (within study groups).

Safety endpoints:

Safety of the study vaccine will be assessed in the Menveo-Menveo and Menactra-Menveo groups and the pooled vaccine group (Menveo-Menveo and Menactra - Menveo) and the vaccine-naive group in terms of the frequencies (percentages) of

¹⁻² Seroresponse is defined for this study as follows: For subjects with pre-vaccination titers < 4, post-vaccination titers 2:16; for subjects with pre-vaccination titers 2:4, post vaccination titers 4 times the pre-vaccination titers.

Name of Sponsor:	Protocol number:	Generic name of study vaccine(s):
GlaxoSmithKline Biologicals S.A	V59 77	Meningococcal (groups A, C, W, and Y) oligosaccharide diphtheria CRM-197 conjugate vaccine
reported adverse events including		

1. Any unsolicited AEs reported within 30 minutes after vaccination;2. Solicited local and systemic AEs reported from Day 1 (6 hours) through Day 7 after vaccination;3. Other indicators of reactogenicity (e.g. use of analgesics/ antipyretics, body temperature) within 7 days after vaccination;4. All unsolicited AEs reported from Day 1 through Day 29 after vaccination;5. Medically-attended AEs, AEs leading to withdrawal and SAEs reported from Day 1 through Day 181 (during the entire study period).		
Statistical Analyses:		
P1: Primary Immunogenicity Objective		
The primary population for the analysis of sufficient immune response is the Per Protocol Set (PPS), and will consist of the Menveo-Menveo group (n=270 evaluable subjects) and Menactra-Menveo group (n=270 evaluable subjects). To demonstrate immune response sufficiency after MenACWY-CRM booster vaccine administration, the lower limit of the one-sided 97.5% Confidence Interval (CI) for percentage of subjects with hSBA seroresponse against each of serogroups A, C, W and Y must be greater than 75%. This will be tested sequentially first in the group of subjects who received primary vaccination with Menveo and, if met, also in the group of subjects who received primary vaccination with Menactra.		
Hypothesis:		
Null hypothesis		Alternative hypothesis
$p_{ij} = 0.75$		$p_{ij} > 0.75$
Where: P_{ij} is the population booster seroresponse rate; $j = 1, 2$ refer to group Menveo-Menveo (first test) and Menactra-Menveo (second test) respectively; $i = 1, 2, 3, 4$ refer to serogroup A, C, W and Y respectively.		

Name of Sponsor: GlaxoSmithKline Biologics S.A	Protocol number: V59 77	Genetic name of study vaccine(s): Meningococcal (groups A, C, W, and Y) oligosaccharide diphtheria CRM-197 conjugate vaccine
Sample Size: Statistical power was estimated based on observed data from study V59P13E1. Assuming the true booster seroresponse rates in the Menveo-Menveo group range from 90% to 97% (alternative hypothesis) for each serotype, a sample size of n=270 will have at least 96% power to show sufficiency of immune response to a booster dose of MenACWY-CRM, compared with a pre-specified reference booster seroresponse of 75% (null hypothesis) using an exact test with 0.025 one-sided significance level. Assuming the true booster seroresponse rates in the Menactra-Menveo group range from 91% to 100% (alternative hypothesis) for each serotype, a sample size of n=270 will have at least 96% power to show sufficiency of immune response to a booster dose of MenACWY-CRM, compared with a pre-specified reference booster seroresponse of 75% (null hypothesis) using an exact test with 0.025 one-sided significance level. Overall statistical power to show sufficiency of immune response to a booster dose of MenACWY-CRM for each serotype in both the Menveo-Menveo and the Menactra-Menveo group will be at least 92%. When taking a 10% dropout rate into account, N=300 previously vaccinated subjects with Menveo and N=300 previously vaccinated subjects with Menactra have to be enrolled in the study. Calculations have been done with nQuery Advisor (Version 7.0).		
Interim Analysis: No interim analysis is planned for this study.		
Data Monitoring Committee: No DMC will be utilized for the study.		

Table4 Time and Events Table

Visit Type	Clinic Visit	Clinic Visit	Phone Call	Clinic Visit	Phone Call	Clinic Visit	Phone Call	Phone Call
	Screening	Treatment	Treatment	Treatment	Treatment	Treatment	Follow- up	Follow- up
Study period								
Study Day		1	3, 5	4/6•	15	29	91	181
Visit Window (Days)	-5 to 1	0	2 days (-1/+1), 4 days (0/+2) after vacc	3/5 days (-1/+1) after vacc	14 days (-2/+2) after vacc	28 days (-7/+14) after vacc	90 days (-14/+14) after vacc	180 days (-14/+14) after vacc
Visit Number	Pre-vaccination	1	N/A	2	3	4	5	6
Study Event	References							
Study Treatment								
Vaccination (vacc)	Section 5.2		X					
Screening and Safety								
Informed Consent"	Section 5.1.1	X						
Medical History	Section 5.1.2	X						
Physical Exam	Sections 5.1.2 and 5.3.1	X	X<		X		X	
Pregnancy Test	Sections 3.5 and 5.1.2	X	X<					
Exclusion/Inclusion Criteria	Section 4	X	X					
Randomization	Section 5.1.4		X<					
30 Minutes Post Injection Assessment	Section 5.2.1		X					

Visit Type Study period Study Day Visit Window (Days) Visit Number	Clinic Visit	Clinic Visit	PhoneCall	Clinic Visit	Phone Call	Clinic Visit	Phone Call	Phone Call
	Screening	Treatment	Treatment	Treatment	Treatment	Treatment	Follow-up	Follow-up
		1	3, 5	4/6	15	29	91	181
	-5 to 1	0	2 days (-1/+1), 4 days(0/+2) after vacc	3/5 da)'S (-1/+1) after vacc	14 da ys (-2/+2) after vacc	28days (-7/+14) after vacc	90days (-14/+14) afel' vacc	180 da ys (-14/+14) after vacc
Study Event	References							
SubjectDiary Dispensed with Training	Section 5.2.1		X					
SubjectDiary Reminder Call	Section 5.2.2			X'	X'			
SubjectDiary Reviewed and Collected	Section 5.3.1						X	
Assess Unsolicited AEs	Section7.1		X		X	X	X	
Assess SAEs	Section 7.1.4		X		X	X	X	X
Assess for medically attended AEs and AEs leading to withdrawal	Sections 7.1.4.I and7.1.3		X		X	X	X	X
Assess relevant medications/ vaccinations	Sections5.1.2 and 6.5	X	X		X	X	X	X

Visit Type	Clinic Visit	Clinic Visit	PhoneCall	Clinic Visit	Phone Call	Clinic Visit	Phone Call	Phone Call
	Screening	Treatment	Treatment	Treatment	Treatment	Treatment	Follow- up	Follow- up
	Study Day	1	3, 5	4/6	15	29	91	181
Visit Window (Days)	-5 to 1	0	2 days (- 1/+1), 4 days (0/+2) after vacc	3/5 da)'S (-1/+1) after vacc	14 days (-2/+2) after vacc	28days (-7/+14) after vacc	90days (-14/+14) afte' vacc	180 days (-14/+14) after vacc
	Visit Number	Pre- vacc.ination	1	NIA	2	3	4	5
Study Event	References							
Imm unogenicity								
Serology blooddraw	Section 3.5		X"		X		X	
Study C-0mp leron Pt ocedure								
Study Tennination	Sec tion 5.5							X
	Notes :							
	
 Subject will be randomized into a blooddraw schedule in a 1:1 ratio. The second clinic visit will occur at Day 4 OR Day 6. 							
	b Confirm consent fonn(s) signed prior to any procedures.							
	' Procedure to be performed prior to vaccination							
	d Reminder for previously vaccinated subjects, appropriate written documentation of the identity of the primary meningococcal vaccination (Menveo or Menactra) and vaccination datemust be provided prior to enrollment.							
	
 If the clinic visit at Day 4 is overlapping withthe specified window of the Day 3 reminder call, the Day 3 reminder call maybe omitted. 							
	If the clinic visit at Day 6 is overlapping with the specified window of the Day 5 reminder call, the Day 5 reminder call maybe omitted							
	f Subjects who tenninate thestudy early are recommended to complete certainstudy-related procedures. See section 5.5 for further details.							

LIST OF ABBREVIATIONS

ACIP	Advisory Committee on Immunization Practices
AE	Adverse Event
CI	Confidence Interval
CBER	Center for Biologics Evaluation and Research
CRM	Cross Reactive material
CRO	Contract Research Organization
EC	Ethics Committee
EoS	End of Study
eCRF	Electronic Case Report Form
EDC	Electronic Data Capture
FAS	Full Analysis Set
FDA	Food and Drug Administration
GCP	Good Clinical Practices
GMR	Geometric Mean Ratio
GMT	Geometric Mean Titer
GSK	GlaxoSmithKlineBiologicals
HIPAA	Health Insurance Portability and Accountability Act
hSBA	Human Serum Bactericidal Assay
IB	Investigator' s Brochure
ICF	Informed Consent Form
ICH	International Conference on Harmonisation of Technical Requirements for Registration of Pharmaceuticals for Human Use
IM	Intramuscular
IRB	Institutional Review Board
LSLV	Last Subject Last Visit
MedDRA	Medical Dictionary for Regulatory Activities
pp	Per Protocol
Ref.	Reference
SAE	Serious Adverse Event
SDAF	Source Documentation Agreement Form
SBIR	Source Data Base for Internet Randomization
SOC	System Organ Class
SOP	Standard Operating Procedure

I. BACKGROUND AND RATIONALE

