3. STUDY DESIGN

3.1 Overview of Study Design

This is a phase 3b, controlled, open-label multi-center study to evaluate safety and immunogenicity of MenACWY-CRM after a single vaccination in healthy individuals who were vaccinated with Menveo or Menactra 4 to 6 years before and in vaccine-naïve individuals.

Study population: Approximately 700 healthy subjects 15 through 55 years of age will be enrolled in the study.

Duration of the study: The duration of this study is approximately 6 months per subject.

Written informed consent and, as applicable according to local guidelines, written assent will be obtained before conducting any study-specific procedures

Vaccination schedule: All subjects will receive a single dose of MenACWY-CRM at Day 1.

Study groups:

Group Menveo-Menveo: approximately 300 subjects, who were vaccinated with a single dose of Menveo 4 to 6 years before, will receive one dose of MenACWY-CRM.

Group Menactra-Menveo approximately 300 subjects, who were vaccinated with a single dose of Menactra 4 to 6 years before, will receive one dose of MenACWY-CRM.

Group Naïve: approximately 100 subjects equally enrolled across all clinical sites, who have not received any meningococcal vaccination, will receive one dose of MenACWY-CRM.

Randomization / Stratification:

Within each study group, subjects will be randomized into one of two different blood draw schedules according to a 1:1 ratio, described as follows:

- Subjects getting blood draws at Day 1, Day 4 and Day 29.
- Subjects getting blood draws at Day 1, Day 6 and Day 29.

For a schematic overview, see [Table 1](#)

Table 3.1-1: Schematic diagram of the VS9_77 study groups

Vaccine History	Vaccination in current study	Blood draw schedule
Menveo N=300	Menveo	Blood draw Day 1, 4, 29 (N=150)
		Blood draw Day 1, 6, 29 (N=150)
Menactra N=300	Menveo	Blood draw Day 1, 4, 29 (N=150)
		Blood draw Day 1, 6, 29 (N=150)
Vaccine-Naive N=100	Menveo	Blood draw Day 1, 4, 29 (N=50)
		Blood draw Day 1, 6, 29 (N=50)

Blinding: open-label study.

Blood samples: Three (3) blood samples of approximately 10 mL each will be collected according to the blood draw schedule in [Table 3.1.1](#).

Data collection: Electronic Case Report Form (eCRF).

Study clinic visits: Three (3) clinic visits at Day 1, Day 4 or Day 6 and Day 29 are planned for each subject.

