4. SELECTION OF STUDY POPULATION

4.1 Inclusion Criteria

In order to participate in this study, all subjects must meet ALL of the inclusion criteria described.

1. Individuals of 18 through 55 years of age on the day of informed consent or assent.
2. Individuals who received Menveo 4 to 6 years prior to enrolment at an age of 11 years or older (Menveo-Menveo group)

OR

Individuals who received Menactra 4 to 6 years prior to enrolment at an age of 11 years or older (Menactra-Menveo group)

OR

Individuals who have not received any previous meningococcal vaccine (Naive group).

3. Individuals who have voluntarily given written informed consent (and/or assent, if applicable) after the nature of the study has been explained according to local regulatory requirements, prior to study entry. If the subject is under age 18 at the time of enrolment, the parent(s)/legal guardian(s) of the subject should have voluntarily given written informed consent.
4. Individuals who can comply with study procedures including follow-up¹.

S. Males

Or

Females of non-childbearing potential²

Or

¹ A subject and/or parent(s)/legal guardian(s) is/are considered to be compliant if the Investigator judges that the subject will complete the Subject Diary and return for all the follow-up visits scheduled in the study.

² A female is considered to be of non-childbearing potential prior to menarche and after natural or induced menopause. Natural menopause is recognized to have occurred after 12 consecutive months of amenorrhea for which there is no other obvious pathological or physiological cause. Induced menopause is recognized to have occurred after hysterectomy, after bilateral oophorectomy, or iatrogenic ablation of ovarian function.

Females of childbearing potential who are using an effective birth control method¹ which they intend to use for at least 30 days after the study vaccination

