5.1.4.2 Study group and treatment number allocation

Enrolled subjects will be randomized in the SBIR system to one of two different blood draw schedules according to a 1:1 ratio, described as follows:

- Subjects getting blood draws at Day 1, Day 4 and Day 29.
- Subjects getting blood draws at Day 1, Day 6 and Day 29.

Allocation of the subject to a blood draw schedules at the investigator site will be performed using a central randomization system on internet (SBIR).

The randomization algorithm will use 3 minimization procedure accounting for the previous vaccination status (Menveo, Menactra or Vaccine-Nai've study group).

For each dose, the study staff in charge of vaccine administration will access SBIR, provide the subject ID, and the system will provide a treatment number consistent with the allocated treatment arms.

SBIR will also be used to ensure adequate and appropriate distribution of enrolment of naïve subjects across all sites.

For any question regarding SBIR, please refer to the SBIR user guide and SBIR Manual for specific instructions. If for any reason, after signing the informed consent form (ICF), the subject who is eligible and enrolled fails to be randomized, this is called a randomization failure and the early termination study procedures must be applied. The reason for all randomization failures should be recorded in the Screening and Enrolment Log and in the source document as specified in the Source Documentation Agreement Form (SDAF). The information on subjects who are randomization failures should be

kept distinct from subjects who are screen failures, as described in [section S.1.2, Screening](#).

If for any reason, after enrolment the subject fails to undergo treatment/study procedures this is an Early Termination and the reason should be recorded in source document as specified in the Source Documentation Agreement (SD.AF). The information on these Early Termination subjects should be kept distinct in the source documentation from subjects who are screen failures, as described in [section 5.1.2, Screening](#).

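### The synopsis promises a Naive group of similar age to the primed groups, but no operative section enforces this and no model adjusts for age, so the descriptive primed-versus-naive contrasts can carry an uncontrolled age difference

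*Protocol*

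**What the plan says.** The age condition appears once in the current protocol, in the synopsis under Study groups: "approximately 100 subjects, of similar age to subjects enrolled in other primed groups, with enrolment distributed across all clinical sites". It is not quantified.

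The other places that define or control the group are these:

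- **Protocol 3.1:** "approximately 100 subjects equally enrolled across all clinical sites, who have not received any meningococcal vaccination". SAP 2 uses the same wording. Neither mentions age.
- **Protocol 3.1, study population:** "Approximately 700 healthy subjects 15 through 55 years of age will be enrolled in the study". Inclusion criterion 1 in 4.1 likewise sets one range for all groups, and criterion 2 identifies naive subjects by vaccine history alone.
- **Protocol 5.1.4.2:** blood-draw allocation uses a "minimization procedure accounting for the previous vaccination status". On naive enrolment it says "SBIR will also be used to ensure adequate and appropriate distribution of enrolment of naïve subjects across all sites".

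On the analysis side, SAP 6.3.1 offers regression-adjusted estimates to deal with baseline differences between groups. The only covariate in the ANCOVA and log-linear models is pre-vaccination titer. SAP 6.3.2 limits subgroups to sex and race, and only for the primary objectives. It also keeps naive summaries unadjusted throughout. SAP 6.1.1 tabulates age by study group.

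**The concern.** The Naive group has two jobs. It supplies the naturally acquired level against which Day 1 persistence is judged, and the first-dose response against which the booster response is compared at Days 4, 6 and 29. Vaccination history is not randomised, so age similarity is one of the few comparability safeguards that the sponsor wrote down for these contrasts.

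A site that follows sections 3 to 5 exactly can enrol naive subjects of any eligible age. Because age similarity is not an entry criterion, elimination code 200 in the SAP (entry criteria not met) would not catch a departure. If age is related to titer or response, part of a primed-versus-naive difference could then be due to age. An enrolment imbalance cannot be undone once the group is full.

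**Working it through.** The plan has no figure to reproduce here. Protocol 8.5 bases the 100 naive subjects on earlier studies and on having 50 per blood-draw schedule, not on a formula. The core check is therefore a comparison of texts.

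| Place | Age condition on Naive group | Site wording |
|---|---|---|
| Synopsis, Study groups | similar to primed groups | distributed |
| Protocol 3.1 | none | equally enrolled |
| Protocol 4.1 | common range only | none |
| Protocol 5.1.4.2 | none | adequate and appropriate distribution |
| SAP 2 | none | equally enrolled |
| SAP 6.3.1 models | age not a covariate | not applicable |

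At Day 1 the pre-vaccination titer is itself the outcome, so the planned covariate cannot adjust the persistence contrast. At Days 4, 6 and 29 it can absorb an age effect that acts through the Day 1 titer, but not a direct effect of age on response.

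**Direction of a possible age difference (illustration).** Assume two strata with midpoints 20 and 40.5 years, and 20% of primed subjects in the older one. The naive-minus-primed difference in mean age is (naive older share − 0.20) × 20.5 years. Naive older shares of 0%, 20%, 50% and 100% give −4.1, 0, +6.2 and +16.4 years. The sign is not determined by the plan.

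**GMT ratio (illustration).** Inputs from the protocol are the group sizes (300 per primed group, 100 naive, each halved between the two blood-draw schedules) and 10% dropout:

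- Days 1 and 29: 300 × 0.9 = 270 per primed group; 100 × 0.9 = 90 naive.
- Days 4 and 6: 150 × 0.9 = 135 per primed group; 50 × 0.9 = 45 naive.

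Assumed, not in the documents: an SD of log10 titer of 0.5 to 0.7, and an age-related shift in the naive GMT of 1.2-, 1.5- or 2.0-fold.

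SE = SD × √(1/n primed + 1/n naive)

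- Days 1 and 29: √(1/270 + 1/90) = 0.1217, so SE = 0.061 to 0.085.
- Days 4 and 6: √(1/135 + 1/45) = 0.1721, so SE = 0.086 to 0.120.

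Dividing log10 of the shift by the unrounded SE (for example 0.3010/0.06086 = 4.9):

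| Assumed shift | log10 | Days 1 and 29, in SE | Days 4 and 6, in SE |
|---|---|---|---|
| 1.2-fold | 0.079 | 0.9-1.3 | 0.7-0.9 |
| 1.5-fold | 0.176 | 2.1-2.9 | 1.5-2.0 |
| 2.0-fold | 0.301 | 3.5-4.9 | 2.5-3.5 |

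If the shift raises the naive GMT, the primed/naive ratio falls by 1 − 1/1.2 = 17%, 1 − 1/1.5 = 33% or 1 − 1/2 = 50%. If it lowers the naive GMT, the ratio rises by 20%, 50% or 100%.

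**Percentage endpoints (illustration).** If response differs by 5 to 20 points between the strata and the older share differs by 30 points, the crude difference moves by 0.30 × 5 = 1.5 to 0.30 × 20 = 6 points.

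**The case against.** The strongest reply is that the synopsis is current protocol text, so its condition is in force. The other sections are silent on age; none waives it. A reader might infer that the later sections revoke the condition. They do not, and what stands is that the condition is stated but not put into operation.

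A reader might also infer that the naive group will be older. Routine vaccination at 11-12 years plus a 4-6 year interval puts routinely primed subjects at about 15 to 18, where unvaccinated people could be scarce. But the documents give neither vaccine uptake nor the primed age distribution, and primed subjects need only have been vaccinated at 11 or older, so they too may be of any age up to 55. No passage gives an effect of age on titer or response. The age difference is possible, not shown.

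The plan also has partial safeguards. Titer-adjusted estimates are planned, and age is tabulated by group, so an imbalance would be seen. Seeing it after enrolment does not prevent it, and the titer adjustment leaves the gaps described above.

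Finally, the stakes are limited. Protocol 8.4.3.3.1 and SAP 7 make these contrasts descriptive, for support or hypothesis generation. Nor would similar age alone make a non-randomised contrast isolate the effect of priming. Both points stand, and they limit the weight of the finding.

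**Conclusion.** The point holds as a gap between a stated comparator property and its implementation. The similar-age condition is in the synopsis only, is undefined, has no enrolment control behind it and no age term in any adjusted model. The Day 1 persistence contrast is the most exposed, because its planned covariate cannot help.

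The consequence is confined to descriptive secondary contrasts. The primary objectives are single-group tests in the two primed groups, and neither they nor their power are touched.

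The size is unknown before enrolment. The standard-error multiples rest entirely on the assumed SDs and fold shifts. They show only that a moderate age effect would not be negligible against sampling error, and less so at Days 4 and 6 than at Days 1 and 29. The change is worth making, but the study's success criterion does not depend on it.

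**What to change.** 1. Repeat the similar-age condition in protocol 3.1, 5.1.4.2 and SAP 2, with a definition such as named age bands and a tolerance.
2. Use one site wording, distributed, in all places. The synopsis and 5.1.4.2 already agree in substance; only 3.1 and SAP 2 say equally.
3. Have SBIR, which already manages naive enrolment by site, also limit it by a few simple age bands consistent with the primed groups. Site quotas proportional to primed enrolment, or caps that track primed accrual, would go beyond what the synopsis asks and are not needed.
4. As a backstop, add age to the ANCOVA and log-linear models and give an age-adjusted Day 1 contrast. This works only where the age distributions overlap, so it supplements the enrolment control and does not replace it.

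The cost is wording in two documents, an SBIR age limit and one covariate that is already collected. No extra subjects are needed. The main downside is that naive recruitment may be slower in the youngest band.
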